### 8.6 Data Management

#### 8.6.1 Obtaining Data Files

The MarketScan® Commercial and Medicare Supplemental medical claims database is part of Amgen's portfolio of licensed data assets.

#### 8.6.2 Linking Data Files

Linking data files will not be necessary for the objectives of this study.

#### 8.6.3 Review and Verification of Data Quality

The MarketScan® Commercial and Medicare Supplemental medical claims database is constructed through collection and standardization of raw data from the appropriate payers, and linking files across time and data type to create a comprehensive and efficient set of database tables. Variables specific to particular employers are added, as are details on clinical information such as therapeutic class, generic product identifier, therapeutic group, etc. Other enhancements are made to improve the data quality and efficiency, for example: updating diagnosis and procedure codes to reflect changes in codes over time if necessary; creating a common synthetic patient identifier that enables patients to be tracked over time and across data types; integrating benefit plan characteristics, enrollment, outpatient pharmaceutical claims, and medical/surgical data. A comprehensive series of edits on the reasonableness and validity of the data are conducted. For example, checking diagnosis against age and gender, charge against payment, and diagnosis and procedure codes against lists of valid values, etc. No data editing, beyond what is applied in the database production process, will be conducted for this study.

- 8.7 Data Analysis
- 8.7.1 Planned Analyses

### 8.7.1.1 Primary Analysis

For the primary analysis, we will describe baseline patient characteristics, and estimate the risk of three CV outcomes (hypertension, stroke, acute MI) in the following four new user cohorts: (1) erenumab-aooe, (2) other mAbs targeting the CGRP pathway, (3) select anti-epileptic medications, and (4) onabotulinumtoxinA. If appropriate based on comparability analyses, we will also separately compare the risk of acute MI and stroke in patients treated with erenumab-aooe to the risk in each of the other three medication cohorts.

### 8.7.2 Planned Method of Analysis

#### 8.7.2.1 General Considerations

All descriptive and comparative analyses will be undertaken in the interactive Casual Studio application. Characterization of patient populations by baseline characteristics is easily accommodated by the software. In addition, the application allows for the estimation of the cumulative risk of a right censored outcome that may be subject to dependent (right) censoring. Overall estimates of risk at various time points, as well as estimates of risk stratified by medical history, demographic characteristics, and medication usage can be presented in both tabular and graphical formats.

A major challenge in observational comparative analyses is the lack of exchangeability, with baseline characteristics that may be unbalanced between study groups and potential differential drop-out across the two arms of the study. Causal Studio is a tool designed to address exchangeability in observational studies. More specifically, the application allows for the estimation of the cumulative risk of a right-censored counterfactual outcome that may be subject to dependent censoring and confounding. Causal Studio is structured as follows: (1) based on user-specified propensity score models and/or censoring models, generate inverse probability of treatment weights (IPTWs) and inverse probability of censoring weights (IPCWs); (2) provide diagnostics (eg, distribution of the propensity score, by treatment groups; and, standardized mean differences between treatment groups for categorical and continuous variables) that enable the user to assess whether the analyses should proceed to the comparative stage, and, if appropriate, (3) execute the structural (ie, weighted) model to estimate the effect of treatment on the outcome. For our purpose, we will use Causal Studio to separately compare the risk of acute MI and stroke in new users of erenumab-acoe versus new users of each of the other three new user comparator cohorts.

## 8.7.2.2 Missing or Incomplete Data and Lost to Follow-up

This study is based on an analysis of automated medical and prescription claims data, and, because claims are collected for the purpose of payment, we assume that diagnoses and prescriptions reported in claims data are a true and accurate reflection of the health status, and medication and health service usage, for an individual. This will not always be true because individuals will sometimes not use medications as prescribed and will not report certain diagnoses. However, for the serious diagnoses, and related medication usage considered here, the presence of an associated claim will be interpreted as indicating that the procedure was conducted, the disease was present,

or the drug was consumed. The absence of a claim will indicate the opposite. As a result, when using claims data for research, missing data will be a concern mainly when lifestyle and biometrics are important for a given analyses because these items are not well captured in claims.

Patient demographics may be missing for a small subset of patients in claims data. Complete case analysis will be used when the overall missing observations (due to missing age and gender) is small. If a combination of these two covariates is missing for 5% or less of the study population, we will adopt a complete case analytic approach. An alternative solution that will be explored to account for the missing data is the use of inverse probability of missing weights, with one weight that would be estimated for missing age, and another weight that would be estimated for missing gender.

The MarketScan® claims database contains death information for a limited number of individuals who died in the inpatient setting. As a result, we assume that information on death is missing in MarketScan®. This missing data presents a challenge in observational studies with long follow-up, where competing risk by death might influence the study results. Our study, with a maximum possible follow-up of ~2.5 years, will be undertaken in a relatively young population, and we assume that the impact of competing risk by death will be minimal.

In claims data, loss to follow-up may occur as a result of plan disenrollment from the MarketScan® database. We will evaluate any loss to follow-up with descriptive statistics, and account for potential differential loss of follow-up with inverse probability of censoring weights.

#### 8.7.2.3 Descriptive Analysis

### 8.7.2.3.1 Description of Study Enrollment

Selection of cohort members will begin by identifying all patients with at least one prescription order for erenumab-aooe, other mAbs targeting the CGRP pathway, selected anti-epileptic medications, and onabotulinumtoxinA, between 17 May 2018 through 31 May 2020 (or, the most recent data available in MarketScan®). Cohort members who meet the inclusion/exclusion criteria for the study will be included in the final analytic data files. Attrition for all four cohorts will be described in a flow chart (Figure 1).

#### Figure 1. Formation of Erenumab-aooe, Other mAb Targeting the CGRP Pathway, SOC Migraine Preventive Medications (anti-epileptics), and OnabotulinumtoxinA Cohorts

### 8.7.2.3.2 Description of Subject/Patient Characteristics

Baseline characteristics, including the most prevalent diagnoses, procedures, and medication class prescriptions will be summarized for the four study cohorts. Descriptive statistics using mean and standard deviation or median and 25th/75th percentile estimates for continuous variables and number and percentages (n, %) for categorical variables will be used to examine patient characteristics.

### 8.7.2.4 Analysis of the Primary Endpoints

For exposition of the descriptive and comparative analytic methods below, we will focus on comparing the effect of erenumab-aooe versus other mAbs targeting the CGRP pathway on the outcome of acute MI, accounting for both confounding and differential loss to follow-up / switching / discontinuation. Note, however, that the same methods will also be applied for the outcome of stroke, for the following comparisons:

- (1) Erenumab-aooe vs other mAbs targeting the CGRP pathway (galcanezumab-gnlm, fremanezumab-vfrm, eptinezumab-jjmr)
- (2) Erenumab-aooe vs selected SOC migraine preventive medications (anti-epileptics) (topiramate, valproic acid, divalproex sodium)
- (3) Erenumab-aooe vs. onabotulinumtoxinA

The technical description of the study analyses below is ordered in the following manner. First, the naïve, unadjusted cumulative incidence (ie, risk) of acute MI is estimated in both new users of erenumab-aooe and new users of other mAbs targeting the CGRP pathway. This first step constitutes the descriptive analyses. Second, the overlap of the propensity score across treatment groups is evaluated, the mean standardized difference for all variables included in the propensity score model is assessed, and a determination is made on whether the negative control outcomes showed treatment associations within the acceptable bounds around the null. Finally, based on these comparability analyses, gated analyses in which the risk of acute MI in new users of erenumab-aooe is compared to the risk of acute MI in new users of other mAbs targeting the CGRP pathway, accounting for both confounding and differential loss to follow-up / switching / discontinuation, will be initiated.

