The naïve, unadjusted cumulative incidence (ie, risk) of hypertension, acute MI, and stroke will be estimated in the following new user cohorts: 1) erenumab-aooe, 2) other mAbs targeting the CGRP pathway, (2) select SOC migraine preventive medications (anti-epileptics), and (3) onabotulinumtoxinA.

Next, the overlap of the propensity score across treatment groups will be evaluated, the mean standardized difference for all variables included in the propensity score model will be assessed, and a determination will be made on whether null findings are or are not estimated for the negative control outcomes chosen for the study. Comparability between erenumab-aooe and each of the other treatment cohorts will be evaluated separately and each of the comparative analyses will be gated. Specifically, the decision to move forward with the comparative analyses for either the acute MI or the stroke outcome will be made after assessment of covariate balance across treatment groups, whether the negative control outcomes showed treatment associations within the accepted bounds around the null, and sufficient sample size to detect a risk ratio of 2.0 or greater. Analyses will proceed only in the treatment pairs where comparability and sufficient sample size are achieved, and not in others.

Based on the comparability analyses and sample size considerations, the risk of acute MI and the risk of stroke will be separately compared across the following three exposure contrasts: (1) erenumab-aooe vs other mAbs targeting the CGRP pathway, (2) erenumab-aooe vs select SOC migraine preventive medications (anti-epileptics), and (3) erenumab-aooe vs. onabotulinumtoxinA. For these gated analyses, we will utilize inverse probability of treatment weights to account for confounding and inverse probability of censoring weights to account for informative censoring.

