### **Comparability Analyses**

### Estimating the Propensity Score

Next, a linear-logistic model for the conditional probability of treatment,  $Pr(A_i=a|L_i)$ , where  $L_i$  is a vector of measured confounders of the exposure and the outcome, as well as risk factors for the outcome, will be fit (Brookhart et al, 2006). The conditional probability of treatment given a set of covariates is commonly referred to as the propensity score (PS).

For the first set of comparability analyses, overlap of the propensity score across treatment groups will be evaluated. Non-overlap in the PS will be addressed with trimming of subjects at the extremes of the PS distribution. In addition, the mean standardized difference for all variables included in the PS model will be estimated. An absolute mean standardized difference > 0.1 for a given confounder or risk factor for the outcome will be used as a measure of potential imbalance (Austin, 2009; Austin et al. 2007). Covariates in the propensity score model with an absolute standardized difference > 0.1 will be examined for potential inclusion in the outcome model or will be used as evidence of insufficient overlap in the distribution of baseline characteristics across treatment groups. Using PS overlap and cut points for the mean standardized difference to make decisions about cohort comparability are part of an iterative process that potentially involves trimming of subjects (because of poor overlap in the PS) and accounting for confounders in the outcome model rather than the exposure model. As such, this process provides guidance on whether cohorts are comparable and contributes additional information to the body of evidence used to determine whether comparative analyses should be initiated or not.

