- Herpes zoster vaccine
- Colon cancer screening
- Visual field tests
- Non-skin cancers
- o Fractures

We will estimate the cumulative incidence (ie, risk) and risk ratios of negative control outcomes for each treatment group comparison, controlling for measured confounders and potential differential loss to follow-up with inverse probability weights. Null

associations between the migraine preventive treatments and the negative control outcome are hypothesized. For this component of the study, an expert panel will guide selection of the final set of negative control outcomes to be used for this study.

We will use Bayesian analyses to provide evidence of treatment group comparability. The negative control effect estimates will be included as inputs (priors) for each treatment comparison, to create a posterior distribution of the bias parameter. Based on the distribution of the bias parameter, we will then estimate the probability that the bias for treatment comparison X vs. Y is less than some threshold. We will subjectively set the threshold for the risk ratio as anything between 0.91 and 1.10 as acceptable, and the Bayesian analysis will provide the posterior probability that the level of bias (unmeasured confounding) is <10% of the null. If this probability is greater than 90% we will proceed with the comparative analysis.

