	9.3.3 Covariates and other characteristics?				
9.4	Is a linkage method between data sources described? (eg, based on a unique identifier or other)			$\boxtimes$	

Secti	on 10: Analysis plan	Yes	No	N/A	Section Number
10.1	Are the statistical methods and the reason for their choice described?				8.7.2
10.2	Is study size and/or statistical precision estimated?	$\bowtie$			8.5
10.3	Are descriptive analyses included?	$\square$			8.7.2.3.2
10.4	Are stratified analyses included?	$\square$			8.7.2.5.2
10.5	Does the plan describe methods for analytic control of confounding?	$\boxtimes$			8.7.2.4
10.6	Does the plan describe methods for analytic control of outcome misclassification?		$\boxtimes$		
10.7	Does the plan describe methods for handling missing data?	$\boxtimes$			8.7.2.2
10.8	Are relevant sensitivity analyses described?	$\square$			8.7.2.5

Secti	on 11: Data management and quality control	Yes	No	N/A	Section Number
11.1	Does the protocol provide information on data storage? (eg, software and IT environment, database maintenance and anti-fraud protection, archiving)		$\boxtimes$		
11.2	Are methods of quality assurance described?	$\boxtimes$			8.8
11.3	Is there a system in place for independent review of study results?		$\boxtimes$		

Sect	ion 12: Limitations	Yes	No	N/A	Section Number
12.1	Does the protocol discuss the impact on the study results of:				
	12.1.1 Selection bias?	$\square$			8.9.1
	12.1.2 Information bias?	$\square$			8.9.1
	12.1.3 Residual/unmeasured confounding?	$\boxtimes$			
	(eg, anticipated direction and magnitude of such biases, validation sub-study, use of validation and external data, analytical methods).				8.9.1
12.2	Does the protocol discuss study feasibility? (eg, study size, anticipated exposure uptake, duration of follow-up in a cohort study, patient recruitment, precision of the estimates)				8.5

Comments:

Sect	ion 13: Ethical/data protection issues	Yes	No	N/A	Section Number
13.1	Have requirements of Ethics Committee/ Institutional Review Board been described?			$\boxtimes$	
13.2	Has any outcome of an ethical review procedure been addressed?			$\boxtimes$	
13.3	Have data protection requirements been described?			$\boxtimes$	

Section 14: Amendments and deviations	Yes	No	N/A	Section Number
14.1 Does the protocol include a section to document amendments and deviations?				11

Section 15: Plans for communication of study results	Yes	No	N/A	Section Number

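### Crude MI and stroke risks by cohort are placed before a comparability decision whose open parts could then be settled with those contrasts in view

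*Protocol*

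**What the plan says.** The Abstract (Data Analysis) begins with the crude risks: "The naïve, unadjusted cumulative incidence (ie, risk) of hypertension, acute MI, and stroke will be estimated in the following new user cohorts". Its next paragraph turns to comparability: "Next, the overlap of the propensity score across treatment groups will be evaluated". Section 8.7.2.4 repeats this order for its worked example. It starts "First, the naïve, unadjusted cumulative incidence (ie, risk) of acute MI is estimated in both new users of erenumab-aooe" and the comparator cohort, continues "This first step constitutes the descriptive analyses. Second, the overlap of the propensity score across treatment groups is evaluated", and ends with the comparison itself. It adds that "the same methods will also be applied for the outcome of stroke, for the following comparisons", and lists all three contrasts. The propensity-score subsection follows the descriptive one and is again introduced as the next step.

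The decision to proceed has fixed and open parts.

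- **Fixed:** acceptable bias between RR 0.91 and 1.10; a posterior probability above 90% that bias lies within those bounds; 15,000 patients per arm for MI and 3,750 for stroke.
- **Open:** the use of propensity overlap and standardized differences is described as "part of an iterative process that potentially involves trimming of subjects (because of poor overlap in the PS"), and it only guides the decision. A covariate above 0.1 may either be considered for the outcome model or count as evidence of insufficient overlap. The decision subsection asks for adequate overlap without a number. Thirteen negative controls are listed as candidates, and "an expert panel will guide selection of the final set of negative control outcomes to be used for this study". No timing is given for that selection.

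**The concern.** The comparability step exists so that the comparative analyses run only where the cohorts can fairly be compared. Its value depends on being settled without reference to the MI and stroke contrasts. In the stated order, whoever makes the open choices (the protocol does not name the decider) may already have seen MI and stroke risk in erenumab users and in each comparator.

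Two things could follow, both within the protocol's wording and without bad faith. A contrast could be judged not comparable partly because its crude result looks odd. Or trimming and the negative-control set could be adjusted further for one contrast than for another. A reader could not then treat a pass or a fail as independent of the safety result.

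**Working it through.** **1. The plan's own figures.** Inputs from the decision subsection of 8.7.2.4 and from Section 8.5: 80% power, alpha 0.05 (two-sided assumed), equal arms, RR 2.0, background rates 0.15 (MI) and 0.60 (stroke) per 100 person-years, taken here as one-year risks.

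- Arcsine formula: n = 2(1.960 + 0.842)² / (2 asin√p1 − 2 asin√p0)². MI (0.0015 vs 0.0030): 15,215. Stroke (0.0060 vs 0.0120): 3,779.
- Events formula: 4(2.802)² / (ln 2)², rounded up to 66 events, divided by p0 + p1. MI: 66/0.0045 = 14,667. Stroke: 66/0.018 = 3,667.

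Both are close to the stated 15,000 and 3,750. The size criterion stands and depends only on patients per arm and an assumed rate, so no observed events are needed to apply it.

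**2. How much the crude step discloses.** Assume one year of full follow-up, the stated rates, and the projected 20,000 erenumab and 23,000 other CGRP mAb users. SE(ln RR) = √(1/e1 − 1/n1 + 1/e0 − 1/n0), where e is events and n is patients.

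| Outcome | True RR | Expected events | Approximate 95% range of crude RR | P(crude RR > 1.5) |
|---|---|---|---|---|
| MI | 1 | 30 vs 34.5 | 0.61 to 1.63 | 0.052 |
| MI | 2 | 60 vs 34.5 | 1.32 to 3.04 | 0.911 |
| Stroke | 1 | 120 vs 138 | 0.78 to 1.28 | 0.001 |
| Stroke | 2 | 240 vs 138 | 1.62 to 2.46 | 0.997 |

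An RR of the size the plan is built to detect would usually be visible at the crude step. This takes the crude RR as equal to the weighted RR; confounding may separate them.

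**3. What selection could do, under an assumed rule.** Take equal arms of 20,000, true RR = 1, one year of full follow-up and crude RR equal to adjusted RR. Suppose only contrasts with crude RR below 1 were opened. The protocol contains no such rule. The mean of ln RR given that it is below 0 is −SE × √(2/π).

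- MI, 30 events per arm: SE = √(2/30) = 0.258; mean ln RR = −0.206; RR about 0.81.
- Stroke, 120 per arm: SE = √(2/120) = 0.129; mean ln RR = −0.103; RR about 0.90.

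**The case against.** The strongest reply has four parts.

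- **Order of exposition.** Section 8.7.2.4 introduces its list as the order of the technical description, which need not be the order in which people see results. This lowers certainty but does not remove the point: the Abstract sets out the same sequence as work to be done, and no passage prevents it.
- **The decision is largely fixed.** The bias bounds, the 90% rule and the sizes are set now, and Appendix D gives an a priori covariate list (additions are allowed). Section 8.7.2.1 runs weights and diagnostics before the weighted outcome model, so the adjusted RR is not seen early. Comparability is judged by treatment pair, which limits picking MI and stroke separately. At its projected 13,000, onabotulinumtoxinA misses the 15,000 MI criterion whatever the crude result. All of this stands and confines the concern to the four open items.
- **Nothing is hidden.** Crude MI and stroke risks are a primary objective and do not depend on the decision. A reader might infer that an unfavourable signal could be suppressed; the protocol does not support that.
- **Details belong in an SAP.** Lock dates and masking often sit there, and their absence here is not the point. The point is the order that the protocol itself states.

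Appendix B, item 11.3 ("Is there a system in place for independent review of study results"), is marked No. It concerns review of results, not who decides on comparability, and adds little.

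**Conclusion.** The point holds in a limited form. As written, crude MI and stroke risks by cohort come before a partly open comparability decision, and the protocol does not separate the two. The exposure is selective opening or tuning of the comparative analyses through trimming, the handling of standardized differences above 0.1, the judgement of overlap, and the choice of negative controls.

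The size of any bias cannot be stated. A reader might take 0.81 (MI) and 0.90 (stroke) as limits on it. They are not: they hold only for true RR = 1 and the other assumptions of step 3. With the same rule and a true RR of 1.5 (45 vs 30 MIs, SE = √(1/45 + 1/30) = 0.236), the mean reported RR would be about 0.91, a factor of 0.91/1.5 = 0.61. Nor does any passage show that the decision would in fact use the crude results.

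**What to change.** Reorder Section 8.7.2.4 and the Abstract as follows.

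1. Describe baseline characteristics.
2. Fix the negative-control set, the trimming rule and the rule for standardized differences above 0.1, and say what overlap is sufficient.
3. Run the overlap, balance and negative-control analyses with MI and stroke by cohort not yet tabulated.
4. Record a dated go/no-go decision for each of the three contrasts and two outcomes. Keep the size criterion on patients per arm as it stands.
5. Then produce the crude MI and stroke risks for all cohorts, and any RR.

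Hypertension has no planned comparison and can be reported at any time. Objectives, data, alpha, power and sample sizes do not change. The cost is a short delay to the descriptive MI and stroke results, one decision record, and some discipline over data access: the data are already licensed to the sponsor, so reordering the text does not by itself keep results from view.
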